## 7.2. **Laboratory Evaluations**

Laboratory data collected during the study will be analyzed and summarized using both quantitative and qualitative methods. Summaries of laboratory data will be provided for the Safety Analysis Set and will include data collected up to the last dose of study drug plus 30 days. The analysis will be based on values reported in conventional units. When values are below the LOQ, they will be listed as such, and the closest imputed value will be used for the purpose of calculating summary statistics as specified in Section 3.7.. SAR-COV-2 PCR result of “Inconclusive” will not be included in numeric summary and will be considered as not negative result for PCR negative confirmation.

A by-subject listing for laboratory test results will be provided by subject ID number and visit in chronological order for hematology, coagulation, and serum chemistry separately. Values falling outside of the relevant reference range and/or having a severity grade of 1 or higher on the DAIDS Grading Scale will be flagged in the data listings, as appropriate.

### 7.2.1. **Summaries of Numeric Laboratory Results**

Descriptive statistics will be provided by treatment group for each laboratory test specified in the study protocol as follows:

- Baseline values
- Values at each postbaseline analysis window
- Change from baseline at each postbaseline analysis window
- Percentage change from baseline to each postbaseline analysis window (if specified)

A baseline laboratory value will be defined as the last nonmissing measurement obtained on or prior to the date/time of first dose of study drug. Change from baseline to a postbaseline visit will be defined as the visit value minus the baseline value. The mean, median, Q1, Q3, minimum, and maximum values will be displayed to the reported number of digits; SD values will be displayed to the reported number of digits plus 1.

In the case of multiple values in an analysis window, data will be selected for analysis as described in Section 3.8.3.

## 7.2.2. Graded Laboratory Values

The DAIDS Table for Grading the Severity of Adult and Pediatric Adverse Event, Version 2.1 (July 2017) will be used for assigning toxicity grades (0 to 4) to laboratory results for analysis. Grade 0 includes all values that do not meet the criteria for an abnormality of at least Grade 1. For laboratory tests with criteria for both increased and decreased levels, analyses for each direction (i.e., increased, decreased) will be presented separately.

For baseline, if both local lab and central lab results are available, central lab results will be selected first for baseline toxicity grade, local lab results will be used when central lab results are missing.

### 7.2.2.1. Treatment-Emergent Laboratory Abnormalities

Treatment-emergent laboratory abnormalities are defined as values that increase at least 1 toxicity grade from baseline at any postbaseline time point, up to and including the date of last dose of study drug plus 30 days. If the relevant baseline laboratory value is missing, any abnormality of at least Grade 1 observed within the time frame specified above will be considered treatment emergent with the exception of Glucose (See [Appendix 2](#) for details.)

### 7.2.2.2. Summaries of Laboratory Abnormalities

Laboratory data that are categorical will be summarized using the number and percentage of participants in the study with the given response at baseline and each scheduled postbaseline visit.

The following summaries (number and percentage of participants) for treatment-emergent laboratory abnormalities will be provided by lab test and treatment group; participants will be categorized according to the most severe postbaseline abnormality grade for a given lab test:

- Treatment-emergent laboratory abnormalities
- Treatment-emergent Grade 3 or 4 laboratory abnormalities

For all summaries of laboratory abnormalities, the denominator is the number of participants with nonmissing postbaseline values up to 30 days after last dosing date.

A by-subject listing of all treatment-emergent laboratory analyses and treatment-emergent Grade 3 or 4 laboratory abnormalities will be provided by subject ID number and visit in chronological order.

Abnormalities in coagulation parameters will be graded for international normalized ratio (INR) and aPTT.

For the international normalized ratio (INR) of prothrombin time (PT) and aPTT, protocol specified toxicity grading scale depends on the upper limit of normal range (ULN). While the ULN of INR and aPTT depends on whether the subject is taking anticoagulant medication or not (ie, Not taking oral anticoagulant: 0.8 – 1.2; Taking oral anticoagulant: 2.0 – 3.0), this information is not collected by the reference laboratory. As a result, INR and aPTT will be graded by assuming subject is not taking an oral anticoagulant, which is a conservative approach that may lead to over-reporting of abnormalities for INR and aPTT.

### 7.3. Body Weight, Vital Signs and Respiratory Status

Descriptive statistics will be provided by treatment group for body weight and vital signs (including heart rate, respiratory rate on room air and blood pressure) as follows:

- Baseline value
- Values at each postbaseline analysis window for rate respiratory rate on room air or at each timepoint for heart rate and blood pressure
- Change from baseline at each postbaseline analysis window for rate respiratory rate on room air or at each timepoint for heart rate and blood pressure

Similar descriptive statistics will be provided by treatment group for SpO2 on room air.

Two types of baseline will be defined for vital signs. An overall baseline value will be defined as the last available value collected on or prior to the date/time of first dose of study drug. Day 1 pre-dose baseline is defined the same as the overall baseline. A pre-dose baseline per day for each of dosing days 2-3 will use the “Pre-infusion” record on that day as baseline. Change from overall baseline to a postbaseline visit and change from pre-dose baseline for dosing days will be defined as the postbaseline value minus the respective baseline value.

In the case of multiple values in an analysis window, data will be selected for analysis as described in Section 3.8.3. No formal statistical testing is planned.

A by-subject listing of body weight, BMI, vital signs (including heart rate, temperature, and blood pressure), and respiratory status (including respiratory rate and SpO2) will be provided by subject ID number and visit in chronological order.

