#### **5.3.2. Infusion-related Reactions**

Infusion-related reactions have been observed during and following administration of RDV. Signs and symptoms may include hypotension, hypertension, tachycardia, bradycardia, hypoxia, fever, dyspnea, wheezing, angioedema, rash, nausea, diaphoresis, and shivering. Slower infusion rates, with a maximum infusion time of up to 120 minutes, can be considered to potentially prevent these signs and symptoms. If signs and symptoms of a severe infusion-related reaction occur, immediately discontinue administration of RDV and initiate appropriate treatment. Please refer to Section [7.6](#).

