### **6.3. Treatment Assessments (Baseline/Day 1, Day 2, and Day 3)**

The following evaluations are to be completed at the Day 1 visit. The investigator must have confirmed eligibility before proceeding with randomization and the Day 1 visit. If the screening and Day 1 visits occur on the same day, no procedures need to be repeated except for clinical laboratory samples that must be collected locally to confirm eligibility. Clinical laboratory samples must be collected at Day 1 to be sent to the central laboratory, even if completed locally, as described in Section 6.7.2. Participants must complete the following assessments before being administered study drug:

- Vital signs (heart rate, temperature, blood pressure) pre-infusion, postinfusion, and when postinfusion observation is completed
- Respiratory status:
  - Respiratory rate
  - Oxygenation: SpO2 on room air
- Complete physical examination (Day 1)
- Clinical symptom-directed physical examination (Day 2, Day 3)
- Review of AEs and concomitant medications
- Review any interactions with health care professionals, other than study staff or designees, including hospitalization; in-person emergency, urgent, or primary care visits; or any other in-person visit attended by the participant and a health care profession. Identify the nature and cause of the visit.

- Obtain blood samples as described in Section 6.7.2 (Day 1, Day 3)
- Nasopharyngeal swab samples for SARS-CoV-2 quantitative reverse transcriptase PCR (RT-qPCR) testing [REDACTED] CCI
- Sputum sample collection from participants with productive cough for SARS-CoV-2 RT-qPCR testing [REDACTED] CCI
- Completion of the COVID-19-adapted FLU-PRO Plus questionnaire (if available)
- Administration of study drug. Instructions on study drug administration are available in a separate manual.

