**Appendix 2. Study Procedures Tablea**

	Screening	Baseline/ Day 1	Day 2	Day 3	Day 7 (± 1 day)	Day 14 (± 1 day)	Day 28 t Follow-up (± 5 days)
Written Informed Consent	X						
Medical History b	X						
Complete Physical Examination c	X	X				X	
Clinical Symptom Directed Physical Examination d			X	X	X		X
Height	X						
Vital Signs e and Weight	X	X f	X f	X f	X	X	X
Respiratory Status g	X	X	X	X	X	X	X
ALT, AST, Serum Creatinine, and Creatinine Clearance/eGFR h	X						
Chemistry i , Hematology j , and Coagulation k Panels		X		X	X	X	
CCI							
Urine Pregnancy Test m	X						
SARS CoV 2 RT qPCR Testing and Potential Resistance Testing n		X	X	X	X	X	
Documentation of SARS CoV 2 Infection	X						
CCI							
CCI							
Medically Attended Visit Information r		X	X	X	X	X	X
FLU PRO Plus Questionnaire s		X	X	X	X	X	
Study Drug Dosing		X	X	X			
Adverse Events and Concomitant Medications	X	X	X	X	X	X	X

a Study visits may be performed in an outpatient setting, at the participant's home via tele health, virtually or remotely, as permitted by local and institutional regulations. The Day 28 visit may be performed via a phone call.

b Medical history will include the date of first symptoms, overall symptoms, exposure source, demographics, baseline characteristics, allergies and all other medical history.

c A complete physical examination must include source documentation of general appearance and the following body systems: Head, neck, and thyroid; eyes, ears, nose, throat, mouth, and tongue; chest (excluding breasts); respiratory; cardiovascular; lymph nodes, abdomen; skin, hair, nails; musculoskeletal; and neurological. Urogenital and reproductive examination should only be completed if clinically indicated.

- d Clinical symptom directed physical examination will include at least cardiac and respiratory evaluation.
- e Vital signs include heart rate, temperature, and blood pressure.
- f On Days 1, 2 and 3, vital signs to be completed pre infusion, postinfusion, and when postinfusion observation is completed; weight from Screening may be used at Days 1-3.
- g Respiratory status includes respiratory rate and SpO2 on room air.

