### **3. GENERAL CONSIDERATIONS FOR DATA ANALYSES**

Analysis results will be presented using descriptive statistics. For categorical variables, the number and percentage of participants in each category will be presented; for continuous variables, the number of participants (n), mean, standard deviation (SD) or standard error (SE), median, first quartile (Q1), third quartile (Q3), minimum, and maximum will be presented.

All statistical tests will be 2-sided and performed at the 5% significance level unless otherwise specified.

By-subject listings will be presented for all participants in the All Randomized Analysis Set and sorted by subject ID number, visit date, and time (if applicable). Data collected on log forms, such as AEs, will be presented in chronological order within the participant. The treatment group to which participants were randomized will be used in the listings. Age, sex at birth, race, and ethnicity will be included in the listings, as space permits.

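### SAP 7.3 gives temperature no by-arm summary, plans no count of participants with a marked post-infusion vital-sign change, and leaves it open whether the two Day 1 post-infusion readings are averaged

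*SAP*

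**What the plan says.** **Collection.** Protocol 6.3 requires, on each dosing day, "Vital signs (heart rate, temperature, blood pressure) pre-infusion, postinfusion, and when postinfusion observation is completed". Note f to the study procedures table in Protocol Appendix 2 repeats the three occasions for Days 1, 2 and 3.

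**Known risk.** Protocol 5.3.2 says of infusion reactions: "Signs and symptoms may include hypotension, hypertension, tachycardia, bradycardia, hypoxia, fever, dyspnea, wheezing", followed by further signs. Heart rate, blood pressure and temperature map directly onto several of these.

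**Summary tables.** SAP 7.3 gives by-arm descriptive statistics for body weight and for "vital signs (including heart rate, respiratory rate on room air and blood pressure", with SpO2 treated similarly. Its bullets cover value and change: respiratory rate by analysis window, heart rate and blood pressure by timepoint. On Days 2 and 3, change is also taken from that day's own pre-infusion value. SAP 3 defines the statistics for continuous variables as n, mean, SD or SE, and "median, first quartile (Q1), third quartile (Q3), minimum, and maximum will be presented".

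**Temperature.** The only mention in SAP 7.3 is in the by-subject listing, which covers "vital signs (including heart rate, temperature, and blood pressure".

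**Day 1.** SAP Table 3-1 has a single post-dose window for Day 1. The note to that table and SAP 3.8.3 apply nominal timepoints to Days 2 and 3 only, and 3.8.3 averages several records that fall on one timepoint. SAP 7.3 refers multiple values in a window back to 3.8.3.

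**The concern.** Readings bracket every infusion, yet the tables use them incompletely in three ways.

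1. Fever is a named reaction sign and temperature is measured three times per dosing day, but no by-arm temperature table is named.
2. For heart rate and blood pressure, the reader gets the centre, quartiles and two extremes of each arm. None of these says how many participants had a marked change. For laboratory data the same SAP does count participants, by worst post-baseline grade (7.2.2.2).
3. Day 1 carries the first and largest dose, and it is the one dosing day without a nominal-timepoint rule. If the reading just after infusion is averaged with one taken after recovery, the acute change is diluted before any statistic is calculated, including the minimum and maximum.

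At stake is how well the vital-sign tables describe acute tolerability of an infusion given to outpatients, some of them at home. Safety in that setting is a primary objective.

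**Working it through.** The documents give no figure on this point, so the check is mainly textual.

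**Text side by side**

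| Item | Collected (Protocol 6.3, Appendix 2) | Planned in SAP |
|---|---|---|
| Heart rate, blood pressure | Three times on Days 1, 2 and 3 | By-arm value and change by timepoint (7.3) |
| Temperature | Three times on Days 1, 2 and 3 | By-subject listing only (7.3) |
| Participants with a marked change | Derivable from the above | Not planned |
| Two post-infusion readings, Days 2 and 3 | Separate | Nominal timepoint (3.8.3) |
| Two post-infusion readings, Day 1 | Separate | One window (Table 3-1); no nominal rule |

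The Day 1 row conflicts with the by-timepoint promise in 7.3 if 3.8.3 is applied as written, and agrees with it only if the programmer carries the nominal rule over to Day 1.

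**Illustration of size**

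Input from the documents: 584 randomized (SAP 2.1.1), so 584/2 = 292 per arm; the number dosed is not given. Assumptions, not in the documents: 9 of 292 (3.1%) have a 30 mmHg fall in systolic pressure, and the change is otherwise normal with mean 0 and SD 10, 12 or 15 mmHg.

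*Mean.* Shift = 9 × 30/292 = 0.92 mmHg. SE of the difference = SD × √(2/292) = 0.83, 0.99 and 1.24. The ratio is 1.1, 0.9 and 0.7, so the mean hides the event.

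*Minimum, readings kept apart.* By simulation, the expected minimum change moves from about −29 to −45 (SD 10), −34 to −48 (SD 12) and −43 to −53 (SD 15). It lies below the 5th percentile of the no-reaction minimum in about 95%, 77% and 45% of runs.

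*Minimum, after averaging with a recovered second reading.* The fall becomes 30/2 = 15 mmHg, and those figures become about 53%, 31% and 17%. The two readings' noise was taken as independent. Changes from a shared baseline would be positively correlated, so averaging would remove less noise while still halving the fall; the independence assumption therefore flatters the averaged analysis. If the fall persists at both readings, averaging loses nothing.

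*Count of participants with a fall beyond a cut.* The 30 mmHg used here is only for arithmetic. Background exceedance is Φ(−30/SD) = 0.13%, 0.62% and 2.3%. Half of the 9 reactors cross, so the expected count with reactions is 4.5 + 283 × background, and without reactions 292 × background:

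| SD | With reactions | Without |
|---|---|---|
| 10 | 4.5 + 0.4 = 4.9 | 0.4 |
| 12 | 4.5 + 1.8 = 6.3 | 1.8 |
| 15 | 4.5 + 6.4 = 10.9 | 6.6 |

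Fisher power for such a comparison is only about 0.1 to 0.4 over cuts of 20 to 30 mmHg. The count is useful as description, because it shows how many participants changed; it is not a sensitive test.

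**The case against.** The strongest reply is that little is hidden. SAP 3 prints the minimum and maximum, so the largest fall and rise in each arm appear, and opposite-direction reactions do not cancel there as they would in a mean. Same-day pre-infusion change is planned. Respiratory rate and SpO2 are summarized too. Protocol 7.5 requires abnormal vital signs with signs or symptoms to be recorded as adverse events when they meet the definition. SAP 7.1.7 counts those per participant and arm, including events that led to stopping study drug. The listing shows every temperature, and the word introducing the list in 7.3 is not strictly exhaustive. The protocol promises no vital-sign outlier table, so nothing is contradicted, and 7.3 plans no formal testing.

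Most of this stands. A reader might infer that the SAP shows only mean-type changes and that acute reactions could not appear at all; the documents do not support that. A reader might also infer that a count would have better than even power. Fisher's test of 3% against 0.5% at 292 per arm does give 0.54, but only by ignoring the ordinary variability assumed for the mean. Nor does any section state that the triple readings exist to detect infusion reactions; that is a reasonable inference from Protocol 5.3.2.

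What the reply does not remove: a minimum shows one participant, not how many; the adverse event route under Protocol 7.5 depends on symptoms, intervention or a change to study drug, and on site reporting; respiratory rate and SpO2 do not follow the pre- and post-infusion schedule; minimum and maximum cannot help temperature without a table; and Day 1 averaging would weaken the extremes themselves.

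**Conclusion.** The point holds in limited form. It is established that temperature is named only for a listing, that no participant-level count of vital-sign change is planned, and that the Day 1 rule is ambiguous. It is not established that the Day 1 readings will be averaged, or that temperature will certainly be left out of the tables.

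The Day 1 ambiguity matters most, because averaging acts before any summary is made: under the assumptions above it cuts visibility through the minimum by roughly half or more. That size rests on an assumed 3.1% frequency, a 30 mmHg fall, SDs of 10 to 15 mmHg, and recovery by the second reading.

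The effect is confined to descriptive safety output. The primary efficacy analysis, the significance level and the sample size are untouched.

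**What to change.** 1. In SAP 3.8.2 (Table 3-1 and its note) and 3.8.3, extend the nominal-timepoint rule to Day 1. Name pre-infusion, postinfusion and end of observation as separate timepoints on all three dosing days, so the two post-infusion readings are summarized separately.
2. In SAP 7.3, add temperature to the by-timepoint summaries of value and change.
3. In SAP 7.3, add a descriptive count and percentage per arm of participants whose largest rise or largest fall from the same-day pre-infusion value, over both post-infusion readings, exceeds an analysis cut. Do this for heart rate, blood pressure and temperature, by dosing day and over Days 1 to 3. Fix the cuts before unblinding and label them as analysis conventions only.

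The cost is SAP wording, one extra table and a few added rows, all from data already collected. The count will include some background exceedances from ordinary variability in both arms, so it should be read against placebo and without a test. No dosing, monitoring or stopping rule changes.

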### 7.4. Prior and Concomitant Medications

Medications collected at screening and during the study will be coded using the current version of the Gilead-modified World Health Organization (WHO) Drug dictionary.

Concomitant medications are defined as medications taken while a participant took study drug. Use of concomitant medications will be summarized by preferred name using the number and percentage of participants for each treatment group. A participant reporting the same medication more than once will be counted only once when calculating the number and percentage of participants who received that medication. The summary will be ordered by preferred term in

descending overall frequency. For drugs with the same frequency, sorting will be done alphabetically.

For the purposes of analysis, any medications with a start date prior to or on the first dosing date of study drug and continued to be taken after the first dosing date, or started after the first dosing date but prior to or on the last dosing date of study drug will be considered concomitant medications. Medications started and stopped on the same day as the first dosing date or the last dosing date of study drug will also be considered concomitant. Medications with a stop date prior to the date of first dosing date of study drug or a start date after the last dosing date of study drug will be excluded from the concomitant medication summary. If a partial stop date is entered, any medication with the month and year (if day is missing) or year (if day and month are missing) prior to the date of first study drug administration will be excluded from the concomitant medication summary. If a partial start date is entered, any medication with the month and year (if day is missing) or year (if day and month are missing) after the study drug stop date will be excluded from the concomitant medication summary. Medications with completely missing start and stop dates will be included in the concomitant medication summary, unless otherwise specified. Summaries will be based on the Safety Analysis Set. No formal statistical testing is planned.

## **7.5. Other Safety Measures**

A data listing will be provided for participants experiencing pregnancy during the study.

## **10. SOFTWARE**

SAS® Software Version 9.4. SAS Institute Inc., Cary, NC, USA.

Phoenix WinNonlin® 8.2. Pharsight Corporation, Princeton, NJ, USA.

## 11. SAP REVISION

Revision Date (DD MMM YYYY)	Section	Summary of Revision	Reason for Revision

## 12. APPENDICES

- Appendix 1. Study Procedures Tablea
- Appendix 2. Programming Specifications

**Appendix 1. Study Procedures Tablea**

	Screening	Baseline/ Day 1	Day 2	Day 3	Day 7 (± 1 day)	Day 14 (± 1 day)	Day 28 t Follow-up (± 5 days)
Written Informed Consent	X						
Medical History b	X						
Complete Physical Examination c	X	X				X	
Clinical Symptom-Directed Physical Examination d			X	X	X		X
Height	X						
Vital Signs e and Weight	X	X f	X f	X f	X	X	X
Respiratory Status g	X	X	X	X	X	X	X
ALT, AST, Serum Creatinine, and Creatinine Clearance/eGFR h	X						
Chemistry i , Hematology j , and Coagulation k Panels		X		X	X	X	
CCI							
Urine Pregnancy Test m	X						
SARS-CoV-2 RT-qPCR Testing and Potential Resistance Testing n		X	X	X	X	X	
Documentation of SARS-CoV-2 Infection	X						
CCI							
Medically Attended Visit Information r		X	X	X	X	X	X
FLU-PRO Plus Questionnaire s		X	X	X	X	X	
Study Drug Dosing		X	X	X			
Adverse Events and Concomitant Medications	X	X	X	X	X	X	X

- a Study visits may be performed in an outpatient setting, at the participant's home via tele-health, virtually or remotely, as permitted by local and institutional regulations. The Day 28 visit may be performed via a phone call.
- b Medical history will include the date of first symptoms, overall symptoms, exposure source, demographics, baseline characteristics, allergies and all other medical history.
- c A complete physical examination must include source documentation of general appearance and the following body systems: Head, neck, and thyroid; eyes, ears, nose, throat, mouth, and tongue; chest (excluding breasts); respiratory; cardiovascular; lymph nodes, abdomen; skin, hair, nails; musculoskeletal; and neurological. Urogenital and reproductive examination should only be completed if clinically indicated.
- d Clinical symptom-directed physical examination will include at least cardiac and respiratory evaluation.
- e Vital signs include heart rate, temperature, and blood pressure.

- f On Days 1, 2 and 3, vital signs to be completed pre-infusion, postinfusion, and when postinfusion observation is completed; weight from Screening may be used at Days 1-3.
- g Respiratory status includes respiratory rate and SpO2 on room air.
- h Obtain ALT (and AST where available), serum creatinine, and creatinine clearance (calculated using Cockcroft-Gault or Schwartz formula; see Protocol Section 6.7.2) if not available within 90 days of screening, using a local laboratory.
- i Chemistry: alkaline phosphatase, AST, ALT, total bilirubin, total protein, albumin, lactate dehydrogenase, creatine phosphokinase, bicarbonate, blood urea nitrogen, calcium, chloride, creatinine, glucose, lipase, magnesium, phosphorus, potassium, sodium, uric acid.
- j Hematology: Complete blood count with differential.
- k Coagulation: INR, PT, aPTT
- l [REDACTED]
- m Urine pregnancy test will only be done for women of childbearing potential.
- n Nasopharyngeal swab and sputum samples will be collected and stored for SARS-CoV-2 RT-qPCR and potential resistance testing.
- o [REDACTED]
- p [REDACTED]
- q [REDACTED]
- r Medically attended visit information includes any interactions with health care professionals other than study staff or designees including hospitalization; in-person emergency, urgent, or primary care visits; or any other in-person visit attended by the participant and a health care profession. Identify the nature and cause of the visit.
- s FLU-PRO Plus questionnaire should be completed daily from Day 1 through Day 14 (if available).
- t Only AEs, symptom assessment, medically attended visit information, and concomitant medications review are needed if the visit is done by phone.

